2.1.2 Current management for local recurrence

Many breast cancer patients would have mastectomy and others would have conservative surgery. However, IBC is generally treated with mastectomy when diagnosed, some locally advanced non-IBC patients with local recurrence who previously underwent breast-conserving surgery might have undergone mastectomy for local recurrence⁷, although many patients with local recurrence would prefer to receive chemotherapy and/or radiation therapy as a salvage treatment because of their inoperable status. Some studies have reported LRR rates following neoadjuvant chemotherapy and breast-conserving surgery to be as high as 26%. More recent reports document rates of 7%-16%, largely equivalent to those seen in patients undergoing initial mastectomy⁸⁻¹⁴. Furthermore, systemic therapy for local recurrence may be preferred for marginally surgical candidates since minor residual disease before radiation therapy is a better prognostic indicator in this population¹⁵, although NCCN guideline defined systemic treatment would be secondary to local treatment. In addition, breast cancer patients with local recurrence frequently have distant metastases, and these patients are candidates for systemic treatment.

2.1.3 Evaluation of treatment effects on locally recurrent breast cancer

A proportion of patients with locally recurrent breast cancer have non-measurable disease. As long as we accrue only patients with locally recurrent breast cancer, we will include those who have only non-measurable local lesions. Defining the overall response rate in this population would be difficult; however, it is reasonable to define the rate of control for measurable and immeasurable disease with PFS and OS. In addition, some biological agents such as imatinib have cytostatic effects on gastrointestinal stromal tumor but lack tumor shrinkage properties; that is, although the size of tumors are similar, the agents induce tumor necrosis. The proposed study agent is expected to induce tumor necrosis and yield overall response rate and disease control rate that is a reasonable surrogate for its efficacy.

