5.1. Inclusion criteria

5.1.1. Histologic confirmation of breast carcinoma.

5.1.2. Histologic confirmation of recurrence of chest wall / cutaneous, subcutaneous or nodal tumors disease with or without distant metastasis.

5.1.3 Patients must have failed at least 1 systemic regimen or have clinical stable disease with capecitabine, hormonal therapy (with or without mTOR inhibitor or CDK4/6 inhibitor), or anti HER-2 therapy (trastuzumab, pertuzumab, ado-trastuzumab emtansine, lapatinib) for at least 2 months after their diagnosis of locoregional/metastatic disease.

5.1.4. Concurrent radiation therapy is permitted after the study treatment is initiated so long as the planned radiation field doesn't overlap with planned injection sites.

5.1.5. Age 18 years or older.

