6.3.3 Dosage Adjustments, Delays, Rules for Withholding or Restarting
If talimogene laherparepvec treatment was delayed by >2 week, that dose will be deemed to have been missed and the subject will proceed to the next scheduled treatment visit.

Dose reductions of talimogene laherparepvec is not permitted, other than a reduction in the volume injected due to a disease response.

If a subject experiences any of the following treatment-related toxicities, talimogene laherparepvec administration should be delayed until the toxicity has resolved to at least CTCAE grade 1 or baseline:

- Grade 2 or greater immune-mediated adverse events, with the exception of vitiligo.
- Grade 2 or greater allergic reactions.
- Any other grade 3 or greater hematologic or non-hematologic toxicity.

Subjects who are receiving talimogene laherparepvec may not receive systemic antiherpetic drugs (eg, acyclovir, valacyclovir, famciclovir), but may receive a topically administered antiherpetic drug more than 20 cm from a talimogene laherparepvec injection site. Dosing should be permanently discontinued if, in the opinion of the investigator, the subject develops clinical evidence of any systemic herpes infection (such as encephalitis or disseminated infection).

If the subject requires corticosteroid dosing of >10 mg prednisone daily (or equivalent, eg, 1.5 mg dexamethasone) for any reason, talimogene laherparepvec dosing must be withheld until the corticosteroid dose has decreased to <10 mg prednisone daily (or equivalent).

Talimogene laherparepvec treatment should be continued based on the potential benefit/risk assessment of the subject.

If talimogene laherparepvec dosing is delayed by more than 6 weeks from the date of the planned dose (i.e., approximately 8 weeks from the previous dose) due to the occurrence of an adverse event that is considered related to talimogene laherparepvec, the subject must be permanently withdrawn from talimogene laherparepvec treatment.

If talimogene laherparepvec dosing is delayed by more than 6 weeks from the date of the planned dose (i.e., approximately 8 weeks from the previous dose) for reasons other than treatment-related toxicity, the case must be reviewed by the principle investigator to determine if the subject can resume talimogene laherparepvec therapy.

Patient will be allowed to continue, capecitabine, hormonal therapy and/or anti-HER-2 therapy while receiving study drug.

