8.0. Evaluation during study

The window for all assessments and treatments should be completed within 5 days of the scheduled time.

Patients will be allowed to continue current hormonal therapy, selected chemotherapy, targeted agents and/or anti-HER-2 therapy, which will be administered as standard of care, (per physician discretion) while receiving study drug.

8.1. Evaluation during talimogene laherparepvec:

- 8.1.1. Patients will have a CBC, differential count and platelet count before each cycle.
- 8.1.2. Patients may repeat the CBC, differential count and platelet count until recovery of these measures before the next cycle (absolute neutrophil counts \geq 1,000 and platelets \geq 100,000 per mm³).
- 8.1.3. Medical history and physical examination with vital signs, weight, and PS before cycles 2 and 5 and every additional 2 cycles of treatments.
- 8.1.4. Digital photography of chest lesions before cycles 2, 5, and every additional 2 cycles of treatment.
- 8.1.5. Toxic effects will be assessed before each cycle.
- 8.1.6. SMA (Na, K, BUN, creatinine, Mg, calcium, AST, ALT, glucose, LDH, and total bilirubin) will be performed before each cycle.
- 8.1.7. Levels of tumor markers (e.g., cancer antigen CA 27.29) will be assessed before cycle 5 and every additional 4 cycles of treatment.
- 8.1.8. Systemic immunity in serum or plasma levels of GM-CSF, IL-2, IL-12, TNF-alpha (α), IFN- alpha (α); and phenotype for T-cell subsets (CD3, CD4, CD8, CD25), and NK-cell subsets (CD16, CD56) will be determined via multiparameter FACS analysis (percentage and absolute numbers) before cycle 5 and at the end of study in [name] laboratory at MD Anderson.
- 8.1.9. PET-CT or CT of bone/ abdomen/chest should be performed before cycle 5 and before every additional 4 cycles of treatment as clinically indicated.
- 8.1.10. Disease assessment will be done at the end of cycle 4, cycle 8 and cycle 10.

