9.6. Criteria for Disease Control

Disease control definition among measurable and non-measurable disease combination

Controlled Disease	Non-measurable disease (i.e., bone)	Measurable disease (i.e., lung, liver, lymph nodes)
Type I measurable disease only	None	CR or PR, or SD \geq 4 months or no true PD (at cycle10)
Type II non-measurable disease only	CR, or SD \geq 4 M	None
Type III Both measurable and non-measurable disease	CR, or SD \geq 4 M	CR or PR, or SD \geq 4 months or no true PD (at cycle10)

A patient with PD of measurable disease prior to end of cycle 10 would be considered to have disease control if the PD is not confirmed at the end of cycle 10.

9.7. Response will not be considered evaluable in the following categories:

9.7.1. Early Deaths: Patients who die within the first 2 weeks of the initiation of drug therapy owing to concurrent disease. These cases will be considered treatment failures in the intent-to-treat analysis.

9.7.2. Lost to Follow-up: Patients for whom there is inadequate information to judge tumor response because of loss of contact with our institution (>2 months after a missed appointment) and with referring physician in spite of repeated attempts to locate them. These cases will be considered treatment failures in the intent-to-treat analysis.

9.7.3. Major Protocol Violation: Patients who significantly deviate from the treatment program by either adding or deleting another agent or another therapeutic maneuver or by modifying substantially the dosage and schedule of the drug under evaluation. Patients who do not fulfill the requirements outlined under Patient Eligibility are also included in this category.

9.8. Down staging is defined as a change in the tumor extent that results in reclassification of the primary tumor and/or regional lymph node metastases into a different (lower) T, N, or M subgroup.

9.9. All subjective toxic effects encountered during the study will be evaluated according to the CTCAE version 4.0. Objective toxic effects will be considered as the maximum numerical deviation from the normal range.

9.10. The survival of patients will be measured from the date of registration.

9.11. Patients will be monitored for 1 year after removal from the study or until death, whichever occurs first. Patients removed from study for unexpected adverse events will be monitored until AE is resolved or stabilized.

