13.3. Secondary endpoints

13.3.1. overall disease control rate, PFS, and OS in all patients

13.3.2. Local overall response rate and disease control rate, PFS, and OS in all patients.

13.3.3. Local overall response rate and disease control rate, PFS, and OS in patients without distant metastases.

13.3.4. Local overall response rate and disease control rate, PFS, and OS in patients with distant metastases.

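### Patients already stable on a drug they continue can count as disease control with no study-drug effect, so the pooled secondary disease control rate and PFS depend on case mix

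*Combined protocol and SAP*

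**What the plan says.** - **Role of disease control.** Section 2.1.3 says the agent should "yield overall response rate and disease control rate that is a reasonable surrogate for its efficacy". The rate is the first secondary objective in 1.2, and 13.3.1 lists "overall disease control rate, PFS, and OS in all patients". Section 13.1 describes the trial's aim as efficacy of the drug as a single agent.
- **Entry.** Criterion 5.1.3 has two limbs joined by 'or'. One is failure of at least one systemic regimen. The other is to "have clinical stable disease with capecitabine, hormonal therapy (with or without mTOR inhibitor or CDK4/6 inhibitor), or anti HER-2 therapy" (named drugs follow) "for at least 2 months after their diagnosis of locoregional/metastatic disease".
- **Continuation.** Section 6.3.3: "Patient will be allowed to continue, capecitabine, hormonal therapy and/or anti-HER-2 therapy while receiving study drug". Section 8.0: "Patients will be allowed to continue current hormonal therapy, selected chemotherapy, targeted agents and/or anti-HER-2 therapy".
- **Scoring.** For measurable disease, 9.6 accepts CR, PR, or stable disease lasting at least 4 "months or no true PD (at cycle10"). For non-measurable disease it accepts CR or stable disease of at least 4 months. Section 9.3 judges stability against the smallest sum since treatment started. Section 9.6 does not say when its 4 months begin.
- **Analysis.** The only split planned in 13.1 is by presence of distant metastases. Section 7.2.2 leaves concurrent medications out of the final analysis, and 12.1 keeps them off the case report form. Section 12.1 collects end dates of earlier treatments but not disease status at entry.

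**The concern.** Patients who enter through the stable limb of 5.1.3 are selected on a feature close to the outcome that 9.6 later scores. If such a patient keeps taking the same drug and nothing changes, she is counted as controlled. The trial has no control arm and no reference rate for disease control, so the analysis cannot separate carried-over stability from an effect of the injections.

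At stake is the meaning of the first secondary objective and of PFS. A respectable pooled DCR could come from an inactive study drug, and its level would move with the mix of entrants. The estimates with and without distant metastases would move in the same way if the share of stable entrants differs between those groups.

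**Working it through.** **The plan's own figures.** The documents give no design figure for disease control. The only operating characteristics are for the primary response rate, and they reproduce. For 0/13 at stage 1 and rejection at 3/35 or fewer, exact two-stage binomial calculation gives:

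- At a true rate of 5%: early stop 0.95^13 = 51.3%, probability of a promising result 8.4%, expected size 13 + (1 − 0.513) × 22 = 23.7.
- At 20%: early stop 0.80^13 = 5.5% (printed as 5%), probability of a promising result 90.3%, expected size 33.8.

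These concern CR and PR only.

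**Timing (6.1: second dose on day 22, then every 2 weeks).** Cycle 10 starts on day 22 + 14 × 8 = 134 and ends on day 147, which is 147/30.44 = 4.8 months.

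**Stable entrants with no study-drug effect.** Assumption: exponential time to progression on the continued drug, with median m of 6 to 12 months. The documents give no such figure. P(no progression by T) = 0.5^(T/m).

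- T = 4 months: 0.5^(4/6) = 0.63; 0.5^(4/12) = 0.79.
- T = 4.8 months: 0.5^(4.8/6) = 0.574; 0.5^(4.8/12) = 0.758.

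**Contribution and shift at the end of cycle 10.** Let f be the share of stable entrants and s0 the rate in all other patients. Both are assumed. Contribution = f × P. Shift caused by the case mix = f × (P − s0), with s0 = 0.20 for illustration.

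| f | Contribution | Shift if s0 = 20% |
|---|---|---|
| 20% | 11 to 15 points | 7 to 11 points |
| 40% | 23 to 30 points | 15 to 22 points |
| 60% | 34 to 45 points | 22 to 33 points |

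For f = 40%: contribution 0.4 × 0.574 = 0.230 to 0.4 × 0.758 = 0.303; shift 0.4 × (0.574 − 0.20) = 0.150 to 0.4 × (0.758 − 0.20) = 0.223. The pooled rate would then be about 35% to 42% instead of 20%, with an inactive study drug.

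**Precision after splitting.** Near a 40% rate the approximate half-width is 1.96 × √(0.4 × 0.6/n): 16 points for n = 35, 21 points for n = 21 (f = 40%, everyone else in one category) and 26 points for n = 14 (f = 60%).

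**The case against.** There is a serious case on the other side, and several parts of it stand.

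- **Stable entrants do not automatically succeed.** A reader might infer that they meet 9.6 by definition. Section 9.3 measures stability from the start of treatment, so the earlier 2 months do not appear to count. On the assumptions above, 24% to 43% of them progress by the end of cycle 10. They can meet the criterion; they need not.
- **The go/no-go decision is untouched.** A reader might infer that the trial could declare the drug promising on carried-over stability. The 0/13 and 3/35 rules use CR and PR, which stability alone cannot produce. Disease control has no threshold or decision rule, and the 2.1.3 sentence names response rate beside it.
- **The two limbs of 5.1.3 are not progressing versus stable.** Failure of a regimen is not dated, and a patient may have failed one regimen and be stable on the next. Splitting by the limb ticked would misclassify such patients.
- **The metastasis results are not formal comparisons.** Section 13.1 plans separate estimates.
- **The stable limb may be narrower than it looks.** Read literally, 5.2.21 excludes chemotherapy and monoclonal antibodies within 28 days of enrollment, and 5.2.22 excludes non-immunosuppressive targeted therapy within 14 days. Against that, 5.1.7 sets blood-count rules for patients already taking some of these drugs, 5.2.2 exempts two of them from the concurrent-therapy exclusion, and neither washout criterion names hormonal therapy. The conflict affects the size of the group but does not show that it is empty.
- **Splitting does not create a control.** Patients progressing at entry may also continue background therapy, and their result remains uncontrolled.

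None of this supplies a way to interpret the pooled rate.

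**Conclusion.** The point holds as a limit on how the pooled secondary DCR and PFS can be read. Under 5.1.3, 6.3.3, 8.0 and 9.6 together, a patient stable on a continued drug can count as disease control with no study-drug effect, and nothing in the analysis plan identifies such patients.

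The size rests on assumptions, because the documents give neither the share of stable entrants nor their expected time to progression. With medians of 6 to 12 months and shares of 20% to 60%, these patients contribute about 11 to 45 points to the DCR at the end of cycle 10. That contribution should not be taken as the bias: the upward shift is the share times the difference from other patients, for example 15 to 22 points at a 40% share with a 20% rate elsewhere.

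The documents do not support extending this to the primary endpoint or its decision rules.

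**What to change.** In 13.1 and on the case report form, record each patient's actual disease status at entry in three categories:

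- (a) documented progression on the most recent therapy;
- (b) stable for at least 2 months on a drug continued during the study, including patients who also failed an earlier regimen;
- (c) other.

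Report the DCR with an exact 95% confidence interval, and Kaplan-Meier PFS, for each category beside the pooled figure. Label the pooled figure and category (b) as descriptive, and do not read either as single-agent disease control. Category (a) is the more informative group, but it is still uncontrolled and should be described so.

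Separately, reconcile the washout exclusions in 5.2.21 and 5.2.22 with 5.1.3, 5.1.7, 5.2.2, 6.3.3 and 8.0, so that it is clear who can enter through the stable limb.

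The cost is one CRF field with a written definition, a few table rows, and a status assessment at entry for patients who qualify through the failure limb, since checking 5.1.3 does not by itself establish it. Intervals widen: near a 40% rate, about ±21 points with 21 patients or ±26 with 14, against ±16 with 35. Recording and reporting entry status changes no eligibility rule, treatment or sample size.

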2.2 Potential anti-breast cancer drug for targeting local disease

Patients with locally recurrent breast disease frequently undergo multimodal treatment at the first occurrence of breast cancer, and because local treatment modalities such as surgical intervention and radiation are difficult to add, they subsequently receive systemic therapy. Talimogene laherparepvec (JS1/ICP34.5-/ICP47-/GM-CSF; OncoVEX^{GM-CSF}) was developed to eliminate solid tumors and has since been considered as a potential treatment option for body surface tumors. In addition to talimogene laherparepvec injected area, this agent would modify immune response and could work on distant metastases. Hence, locally recurrent breast disease matches as target disease for talimogene laherparepvec regardless of concomitant distant metastases, hence talimogene laherparepvec is possible new local treatment option.

3.0 Rationale

Local recurrence of breast cancer can result in substantial morbidity and also frequently leads to systemic metastases. Modalities used to treat locally recurrent breast cancer include chemotherapy, hormone therapy, radiation therapy, and surgery. Compared with distant metastases, local recurrence is staged as possible curative status if additional surgery is available, however this opportunity is limited for patients with minor local disease having had conservative

surgery. In addition, survival improvement has not well been demonstrated due to lack of new modality of local treatment.

Current treatment modalities for locally recurrent breast cancer depend on the operability of lesions, disease aggressiveness, previous chemotherapy or radiation therapy, and histologic subtypes; thus, a new modality for treating local disease is needed, since systemic therapy is currently the last resort intervention. Talimogene laherparepvec is immunotherapy with a dual mechanism of generating local tumor lysis and systemic antitumor immune response. In a previous phase I study, talimogene laherparepvec as a single agent was shown to induce tumor necrosis in breast cancer.

The purpose of this study is to determine the local and systemic antitumor efficacy of talimogene laherparepvec in locally recurrent breast cancer patients with or without distant metastases, as evidenced by improved overall response rates. This will be the first study to use biopsy of distant disease to demonstrate whether systemic immune modulation has antitumor efficacy in breast cancer patients. We will also evaluate the antitumor effects of talimogene laherparepvec via comprehensive imaging such as chest x-ray, ultrasound, computed tomography (CT), and positron emission tomography ¹⁶CT as clinically indicated. In addition, we will conduct multiple biological correlative studies to understand the role of immune response activated by talimogene laherparepvec in breast cancer. Patients with initially inoperable local recurrence can be candidates for surgery with curative intent if their tumors become operable.

4.0 Product drug information

4.1 Mechanism of action of talimogene laherparepvec

[figure not shown]
Talimogene laherparepvec, which is a genetically modified HSV type 1 (HSV1), has dual mechanisms for eliminating solid tumors (Figure 2). First, HSV1 in which the neurovirulence factor ICP34.5 is inactivated has the potential to cause tumor lysis in several tumor models. Second, ICP47 deletion via the up-regulation of US11, which occurs following this mutation, functions to block antigen processing in HSV-infected cells, so the immune stimulating properties of the virus are expected¹⁷. In addition, US11 gene expression enhances tumor-selective viral replication¹⁸, and GM-CSF is a potent immune stimulator and enhances immune response¹⁷ by activating dendritic cell and promoting antigen presentation to CD4+ or CD8+ T cells. Activated CD8+ cytotoxic T cells are expected to offend distant tumor cells. The infected neoplastic cells are killed via replicating virions, and release them. As viruses kill neoplastic cells, cross-resistance with other treatment modalities, such as chemotherapy, hormonal therapy, and radiation therapy, does not arise. Thus, immunotherapy could complement current standard treatment options.

Oncolytic replication-competent HSV can infect and kill tumor cells, but normal cells are not terminated by the cytopathic effects of HSV, as shown in an in vitro investigation of the efficacy and toxicity of oncolytic HSV in breast cancer¹⁹. A phase 1 study of talimogene laherparepvec (14 cases of breast cancer out of 30 total cases)¹⁸, revealed no major responses in any cases, including melanoma; however, four patients with breast cancer had local disease stabilization. In the phase 1 study, talimogene Laherparepvec was shown to be effective up to 6 cm from the

injection site. Considering side effects and viral replication, the investigators concluded that talimogene laherparepvec injections every 2-3 weeks were appropriate for future clinical trials.

Figure 2: Mechanism of talimogene laherparepvec against local and distant tumor²⁰

Injected directly in tumor mass.

[figure not shown]
Talimogene laherparepvec (OncovEX^{GM-CSF}) is attenuated herpes simplex virus type 1 (HSV) and modified to replicate only in tumor cells. This has two separate treatment strategies and the first is oncolytic potential due to amplified HSV in tumor cells. After the tumorlysis occurred, talimogene laherparepvec activate dendritic cells with GM-CSF effect, and antigen would be presented through dendritic cell to CD4+ and CD8+ T cells. Activated CD8+ cytotoxic T-cell induces systemic immunity for breast cancer located at distant organ as second option.

